A secondary objective of the study was to assess efficacy at each dose level based on (1) change in SARS-CoV-2 viral load from baseline (Day 1 prior to start of the study treatment) measured at Days 4, 7, 15, and 31; (2) time from baseline until undetectable SARS-CoV-2 viral load by reverse transcription polymerase chain reaction (RT-PCR); (3) mortality at Days 7, 15, and 31; (4) percentage of patients requiring invasive mechanical ventilation and/or ICU admission at Days 7, 15, and 31; (5) percentage of patients requiring non-invasive mechanical ventilation at Days 7, 15, and 31; and (6) percentage of patients requiring oxygen therapy at Days 7, 15, and 31. Results of these assessments, summarised in [Table 3](#), showed comparable results across the three dose groups. As progressive deterioration of respiratory function and development of cytokine release syndrome typically occur at a mean of 10 days from onset of COVID-19 symptoms⁴⁴, the endpoint of hospital discharge by Day 15 is considered to reflect successful amelioration of life-threatening complications.

Considering that dose groups were reasonably balanced for baseline characteristics, including age, gender, time from symptom onset to randomisation, comorbidities associated with increased susceptibility to complications from COVID-19 infection, disease severity at baseline, vital signs and laboratory assessments at baseline, and viral load at baseline, post-hoc analyses were performed to identify factors associated with hospital discharge by Day 15. Logistic regression analyses performed to assess a wide range of covariates for correlation with hospital discharge by Day 15 found that only the covariate of viral load at baseline was significantly correlated with

discharge rate. Additionally, covariates of 2.5-mg plitidepsin dose and age showed correlations that nearly reached significance. Consistent with results from the logistic regression analyses, differences in viral load at baseline were significantly correlated with efficacy outcomes, including use of oxygen therapy, use of invasive and non-invasive mechanical ventilation, and death, but viral load at baseline was not correlated with disease severity at baseline.

Among patients with moderate severity COVID-19 infection (N=23), log-rank analysis of the probability of hospital discharge as a function of plitidepsin dose indicated a dose-related increased in discharge by Day 8, with 100% (8/8) of patients treated with 2.5 mg/day plitidepsin discharged by Day 8 compared with 57% (4/7) treated with 2.0 mg/day and 62% (5/8) treated with 1.5 mg/day.

Table 3: Summary of Protocol-specified Efficacy Endpoints in Study APLICOV-PC

Endpoint	Dose Cohort			
	1.5 mg N=14 ^A	2.0 mg N=15	2.5 mg N=15	Total N=44
Patients discharged from hospital	n (%)			
Day 1 to Day 7	3 (21.4)	2 (13.3)	5 (33.3)	10 (22.7)
Day 1 to Day 8	6 (42.9)	9 (60.0)	10 (66.7)	25 (56.8)
Day 9 to Day 15	5 (35.7)	5 (33.3)	1 (6.7)	11 (25.0)
Day 1 to Day 15	11 (78.6)	14 (93.3)	11 (73.3)	36 (81.8)
Day 1 to Day 31	13 (92.9)	14 (93.3)	13 (86.7)	40 (90.9)
Mortality from Day 1 to				
Day 7	---	---	---	---
Day 15	---	---	---	---
Day 31 ^B	1 (7.1)	---	1 (6.7)	2 (4.5)
Patients requiring invasive mechanical ventilation and/or ICU admission				
Day 1 to Day 7	2 (14.3)	1 (6.7)	2 (13.3)	5 (11.4)
Day 8 to Day 15	1 (7.1)	1 (6.7)	1 (6.7)	3 (6.8)
Day 16 to Day 31	1 (7.1)	1 (6.7)	1 (6.7)	3 (6.8)
Day 1 to Day 31	2 (14.3)	1 (6.7)	3 (20.0)	6 (13.6)
Patients requiring non-invasive mechanical ventilation				
Day 1 to Day 7	4 (28.6)	0	1 (6.7)	5 (11.4)
Day 8 to Day 15	3 (21.4)	0	2 (13.3)	5 (11.4)
Day 16 to Day 31	1 (7.1)	1 (6.7)	1 (6.7)	3 (6.8)
Day 1 to Day 31	5 (35.7)	1 (6.7)	2 (13.3)	8 (18.2)
Patients requiring oxygen therapy at				
Day 7	12 (85.7)	12 (80.0)	11 (73.3)	35 (79.5)
Day 15	4 (28.6)	1 (6.7)	4 (26.7)	9 (20.5)
Day 31	0	2 (13.3)	1 (6.7)	3 (6.8)
Days 1 to 31	12 (85.7)	12 (80.0)	11 (73.3)	35 (79.5)
Mean change in viral load from baseline to ^C	\log_{10} copies/mL			
Day 4	-1.23	-1.49	-1.32	-1.35
Day 7	-2.55	-2.26	-2.25	-2.35
Day 15	-4.22	-2.70	-2.92	-3.25

Day 31	-4.70	-3.53	-3.49	-3.85
Mean time from baseline until undetectable viral load ^c	11	14	14	13

Abbreviations: --- = no events reported; ICU = intensive care unit

A: Patient who experienced an anaphylactic reaction during the first plitidepsin infusion had treatment discontinued and was not considered evaluable for efficacy

B: One additional patient treated at 2.5 mg/day died on Day 57, because of COVID-19 complications.

C: Results based on 42 patients at Day 4 (13 at 1.5 mg, 14 at 2.0 mg, 15 at 2.5 mg), 40 patients at Day 7 (13 at 1.5 mg, 14 at 2.0 mg, 13 at 2.5 mg), 38 patients at Day 15 (12 at 1.5 mg, 13 at 2.0 mg, 13 at 2.5 mg), and 39 patients at Day 31 (11 at 1.5 mg, 14 at 2.0 mg, 14 at 2.5 mg)

1.3. Benefit-risk Assessment

In the APLICOV-PC study, most patients (87%) had moderate-to-severe disease and 82% of patients were discharged by Day 15. As progressive deterioration of respiratory function and development of cytokine-release syndrome typically occur at a mean of 10 days from onset of symptoms,⁴⁴ the endpoint of hospital discharge rate at Day 15 is considered to reflect successful amelioration of life-threatening complications. Post-hoc analyses showed that only baseline viral load was significantly correlated with hospital discharge by Day 15.

In the APLICOV-PC study, median baseline viral load was 6.1 (1.5 to 10.6) \log_{10} copies/mL a mean $-3.25 \log_{10}$ reduction in viral load was observed by Day 15. These results support the conclusion that plitidepsin reduces viral replication.

However, among patients with moderate disease at baseline, log-rank analysis showed a dose-response effect, with 100% (8/8) treated with 2.5 mg/day plitidepsin discharged by Day 8 compared with 57% (4/7) treated with 2.0 mg/day and 62% (5/8) treated with 1.5 mg/day.

Considering the low rate of drug-related Grade ≥ 3 AEs and the high discharge rate at Day 15, along with an average $3.25 \log_{10}$ reduction in baseline viral load by Day 15, evidence to date indicates a positive benefit-risk for plitidepsin for treatment of patients hospitalised for COVID-19 infection and justifies conducting a randomised, controlled trial to establish tolerance and efficacy.

As plitidepsin is a substrate of cytochrome P450 3A4 (CYP3A4), strong inhibitors and inducers of CYP3A4 should not be co-administered with plitidepsin unless there is no therapeutic alternative. Moderate inhibitors and inducers of CYP3A4 should be used with caution in combination with plitidepsin ([Appendix 4 – Inhibitors and Inducers of CYP3A4](#)).

Additional information about risks based on preclinical findings, clinical findings, and AEs of special interest are provided in the IB.

2. OBJECTIVES AND ENDPOINTS

2.1. Objectives

Primary objective

- To compare efficacy of plitidepsin 1.5 mg or 2.5 mg *versus* the control assessing the need of supplementary oxygen.

Key secondary objective

- To compare efficacy of plitidepsin 1.5 mg or 2.5 mg *versus* the control assessing the time to sustained hospital discharge.

Secondary Objectives

- To compare efficacy of plitidepsin 1.5 and 2.5 mg *versus* control:
 - Assessing clinical status by the 11-category WHO Clinical Progression Scale⁴⁵ (See [Appendix 13 - World Health Organization \(WHO\) Clinical Progression Scale](#)).
 - In terms of the need of advanced oxygen support.
 - In terms of need for intensive care support.
- To compare safety/tolerability of plitidepsin 1.5 mg or 2.5 mg *versus* the control in terms of:
 - adverse events, adverse reactions and mortality.
 - abnormal laboratory parameters.
 - variations of vital signs.
 - ECG variations.

Other secondary objectives

- To compare efficacy of plitidepsin 1.5 mg or 2.5 mg *versus* the control in terms of:
 - hospital readmission related to COVID-19.
 - clinical evolution.
 - the need of supplementary oxygen.
 - the need of intensification of respiratory or intensive care support.
 - the need of intensification of pharmacological therapies.
 - superinfections.
 - mortality.
 - the evolution of viral load.
 - the evolution of inflammatory markers.
 - the immune response against SARS-CoV-2.
- To compare efficacy in the primary endpoint and describe safety/tolerability of pooled plitidepsin arms *versus* control.
- To compare efficacy in the primary endpoint and describe safety/tolerability between plitidepsin arms (1.5 *versus* 2.5 mg) in case both are significantly superior to the control.

- To explore the influence of risk factors or scores for clinical deterioration that were not individually included.
- To compare the results obtained before and after the change of the primary and secondary endpoint (protocol v.6 *versus* v.7).

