A total sample size of 609 patients (203 in each arm) with 530 events necessary for the analysis of the primary endpoint has been calculated based on assumptions of a 1-sided type I error of 1.25% ($\alpha=0.0125$) with at least 80% power ($\beta=0.2$) to detect target hazard ratio (HR) of 1.4 in the time to sustained withdrawal of supplementary oxygen, which means a decrease in the median time to the event from 8 days⁴⁸ (control arm) to 5.7 days (plitidepsin). This sample size is adjusted for the multiple comparisons of each plitidepsin arm with control group by a Bonferroni adjustment. At the final analysis, if the HR is 1.27 or greater, in favour of any plitidepsin arm (equivalent to a decrease in the median time to sustained withdrawal of supplementary oxygen of 1.7 days or greater), then it is expected that the null hypothesis (i.e., $HR \leq 1$) will be rejected.

A futility analysis for efficacy/safety will be performed when 33% of events (sustained withdrawal of supplementary oxygen) have been reached. The rho family of beta-spending functions ($\rho=1.18$) will be used for the calculation of the stopping boundaries for futility in order to control type II error. The stopping boundaries for the futility analysis will be calculated with the actual number of events available in the ITT population at that moment; if the number of

events at the futility analysis is 116 in a pair comparison, the beta-spending corrected p-value to reject the alternative hypothesis should be higher or equal than 0.4199 and this p-value is associated with a $HR \leq 1.0382$.

If the recommendation of the IDMC is to discontinue one of the plitidepsin dosing arms at this futility analysis following the stopping rules, the study will continue from that point on a 1:1 randomisation fashion until the completion of the remaining treatment arms (203 patients per arm and 353 events of sustained withdrawal of supplementary oxygen in total necessary to perform the final analysis). The patients still ongoing in the dropped arm would continue to be followed up as per protocol.

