8.2.1. Intent-to-Treat (ITT) Population

All patients randomised in the trial, regardless of whether they received treatment.

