8.5.1. Primary Efficacy Outcome Measures

Time-to event data (time to sustained withdrawal of oxygen supplementation) will be analysed using the Kaplan Meier method and presented with 95% CIs. A Cox regression model, including the levels of the randomisation stratification factors as covariates, will be applied to compare results between each dose of plitidepsin *versus* control arm. Hazard ratios, 2-sided 95% CIs, and p values for the comparison of each dose of plitidepsin *versus* control arm will be presented. The time-to-event between each dose of plitidepsin *versus* control arm will be compared using a 2-sided stratified log-rank test. The model will be adjusted for the randomisation stratification factors, i.e., Geographical Region (Europe *versus* Rest of the World), Charlson Comorbidity Index (0-1 *versus* >1) ([Appendix 11- Age-adjusted Charlson Index](#)) and Barthel index (≥ 90 *versus* <90) ([Appendix 7 – Barthel Index for Functional Assessment](#)). An unstratified log-rank test and Cox regression model will also be analysed as a sensitivity analyses. For both stratified and unstratified models, the hazard ratios, 2-sided 95% CIs, and p-values for the comparison of each dose of plitidepsin *versus* control arm will be presented. Proportional hazard assumption will be checked by means of a Cox regression including treatment and its interaction with time.⁴⁹ In case of strong rejection of proportionality, then restricted mean survival estimates and weighted log-rank tests (if applicable) will also be calculated in a sensitivity analysis in addition to HR.⁵⁰ The main analysis will be adjusted for multiplicity using the Hochberg step-up procedure to preserve the type I error rate in the comparison of each dose of plitidepsin *versus* control arm. If the accrual in any of the experimental arms is stopped after the interim futility analysis, the final analysis for the primary endpoint in the remaining arms will be performed at the 1.25% level using a Bonferroni-adjusted type I error rate.

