8.9. Futility Analysis

A futility analysis for efficacy/safety will be performed when 33% of events (sustained withdrawal of supplementary oxygen) have been reached. The rho family of beta-spending functions (with $\rho=1.18$) will be used for the calculation of the stopping boundaries for futility in order to control type II error. The stopping boundaries for the futility analysis will be calculated with the actual number of events available in the ITT population at that moment; if the number of events at the futility analysis is 116 in a pair comparison patients, the beta-spending p-value to reject the alternative hypothesis should be higher or equal than 0.4993 and this p-value is associated with a $HR \leq 1.0382$.

If the recommendation of the IDMC is to discontinue one of the plitidepsin dosing arms at this futility analysis following the stopping rules, the study will continue from that point on a 1:1 randomisation fashion until the completion of the remaining treatment arms (203 patients per arm and 353 events of sustained withdrawal of supplementary oxygen in total necessary to perform the final analysis). The patients still ongoing in the dropped arm would continue to be followed up as per protocol and a Bonferroni-adjusted type I error rate of 1.25% will be kept for the comparison of the primary endpoint between the remaining plitidepsin arm and the control arm.

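### If one dose is closed at the futility look, the pooled-plitidepsin versus control comparison mixes a 2:1 and a 1:1 period with no period term, so about one sixth of any shared time trend enters the pooled HR

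*Protocol*

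**What the plan says.** - **Objective.** Protocol Section 2.1, under other secondary objectives: "To compare efficacy in the primary endpoint and describe safety/tolerability of pooled plitidepsin arms" versus control. No condition is attached. The next objective, 1.5 mg versus 2.5 mg, is conditional on both doses beating control.
- **Allocation.** Section 5.2 randomises 1:1:1. If a dose is stopped for futility, Section 8.9 says "the study will continue from that point on a 1:1 randomisation fashion until the completion of the remaining treatment arms", with 203 patients in each remaining arm.
- **Population.** Section 8.5 analyses time-to-event endpoints in the ITT population, which Section 8.2.1 defines as "All patients randomised in the trial, regardless of whether they received treatment".
- **Model.** Section 8.5.1: "The model will be adjusted for the randomisation stratification factors", namely region, Charlson index and Barthel index. Section 8.5.3 carries similar methods over to the other secondary endpoints.
- **After a drop.** Sections 8.5.1 and 8.9 describe the final primary analysis for the remaining arms only, at 1.25%. They do not say how the pooled comparison should then be done.

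**The concern.** Within each period the randomisation is sound. Across periods the pooled plitidepsin to control ratio differs, so treatment group becomes associated with time of randomisation. A model with no period term then attributes part of any change in recovery over time to plitidepsin.

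The protocol gives reasons to expect such change. Accrual runs about 20 months, supportive care follows NIH or local guidelines, and subgroups are planned by viral variant, vaccination status and protocol version (v.6 versus v.7). None of these is tied to the allocation change, and a subgroup table does not correct a pooled estimate.

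At stake is the pooled HR for the primary endpoint and its p-value. The error could go either way: slower late recovery flatters plitidepsin, and faster late recovery counts against it.

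**Working it through.** **1. Reproducing the plan's figures.** Section 8.1 gives "a 1-sided type I error of 1.25" per cent, "with at least 80% power", "to detect target hazard ratio (HR) of 1.4" and "a decrease in the median time to the event from 8 days" on control.
- Schoenfeld events for one pair: 4 × (2.2414 + 0.8416)² / (ln 1.4)² = 336.
- With a non-binding futility look at 116/353 and beta spending 0.2 × t^1.18, 353 events give power 0.800, futility p = 0.4196 and HR 1.0384. The plan states 0.4199 and 1.0382.
- Critical HR: exp(2 × 2.2414/√353) = 1.27, as stated.
- Three arms: 353 × 1.5 = 529.5, i.e. 530.

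The plan's event counts and boundary therefore reproduce. (Section 8.9 prints 0.4993 with the same HR. The check uses the 0.4199 of Section 8.1.)

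**2. Number randomised at closure.** The protocol does not give this. At 353/406 = 0.869 events per patient, 116 pair events correspond to 116/(2 × 0.869) ≈ 67 patients per arm. More will be randomised while the look is done. Assumed range: 70 to 110 per arm.

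**3. Share of a trend that enters the pooled HR.** Let n be the number per arm at closure. The late share is (203 − n)/203 in controls and (203 − n)/(203 + n) in pooled plitidepsin.

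| n | Controls late | Pooled late | Difference d |
|---|---|---|---|
| 70 | 133/203 = 0.655 | 133/273 = 0.487 | 0.168 |
| 90 | 113/203 = 0.557 | 113/293 = 0.386 | 0.171 |
| 110 | 93/203 = 0.458 | 93/313 = 0.297 | 0.161 |

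So d is about one sixth. For the remaining dose versus control, both late shares are (203 − n)/203, so d = 0.

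**4. Bias with no drug effect.** If h is the late-to-early recovery hazard, the pooled HR is approximately exp(−d × ln h). At n = 90:
- h = 1/1.2: exp(0.171 × 0.182) = 1.03
- h = 1/1.4: exp(0.171 × 0.336) = 1.06

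The sizes of h are assumptions. The value 1.4 is the plan's target treatment HR, borrowed as a scale for a shared change.

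**5. Simulation.** Exponential recovery with early median 8 days, 6% never recovering, censoring at Day 30, 70 to 110 per arm at closure, 4,000 trials per setting, no drug effect, pooled log-rank test without period. Error is one-sided at nominal 2.5%.

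| Late/early hazard | Pooled HR | Error, all trials | Error, given exactly one dose met futility |
|---|---|---|---|
| 1/1.2 | about 1.03 | about 4% | about 3% |
| 1/1.4 | about 1.05 | about 7% | about 5% |

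The HR and all-trials columns take one dose as closed whatever its interim result. In the last column the look is taken at 62 patients per arm. The reference there is about 1% to 2%, which is what results with no drift or with period stratification.

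**6. Larger drift and the remedy.** A second simulation used 33% to 50% randomised at the switch, all patients able to recover, and 3,000 trials per setting.
- Drift 1/1.5: pooled HR 1.07, one-sided error 9% to 10%.
- Drift 1.5: pooled HR 0.93 to 0.94.
- Stratified by period, under either drift: pooled HR 0.997 to 0.999, error 2.0% to 3.1% in either tail, consistent with 2.5%.
- Remaining dose versus control: HR 0.999 to 1.000 throughout.

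**The case against.** **The SAP may cover this.** Section 8 leaves details to the SAP, Section 8.5.3 says only that similar methods apply, and the synopsis allows Cox models with further prognostic factors. That is fair, and a period term could be added there. But the protocol itself fixes the unconditional objective, the allocation change, the full ITT set and the named adjustment factors. Followed as written, these produce the confounding.

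**The stakes are low.** This stands. The problem arises only if exactly one dose is dropped. It concerns a comparison outside the Hochberg and Bonferroni provisions, and pooled safety is only to be described. Placing the whole change at arm closure, as the simulations do, is also the worst timing.

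**Two stronger readings are tempting, and the document does not support them.**
- A reader might infer that any shared change over time is counted in full as a treatment effect. Only about one sixth of it on the log scale reaches the pooled HR.
- A reader might infer, from the reference to each dose in Section 8.5.1 plus the ITT definition, that the dropped dose will finally be compared with all controls, where the bias would be much larger. No section states such a comparison. Sections 8.5.1 and 8.9 speak of the remaining arms after a drop. Error rates for it that ignore the futility rule would mostly describe trials in which the dose would not have been dropped. None should be quoted against this plan.

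**Conclusion.** The point holds for the pooled-versus-control comparison of the primary endpoint when exactly one dose is closed. The pooled HR with no drug effect moves to about 1.03 to 1.05 under a late-to-early recovery hazard of 1/1.2 to 1/1.4, and below 1 if late recovery is faster. One-sided error at nominal 2.5% rises to about 4% to 7%, or about 3% to 5% once the futility rule is taken into account. These sizes rest on an assumed step change at closure and an assumed 70 to 110 patients per arm at that time. The share of about one sixth is almost insensitive to the latter. The confirmatory comparison of the remaining dose with control is not affected. This is a minor point about a secondary analysis.

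**What to change.** Add to Sections 8.5.1 and 8.9: if an arm is closed, the pooled plitidepsin versus control comparison will be stratified by randomisation period (before or after closure), in addition to the randomisation factors. If the closed dose is compared with control at all, only controls randomised while that dose was open will be used.

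The rule should be fixed before any unblinded futility data exist. It costs one extra stratum derived from the randomisation date, and some loss of precision for the closed dose because later controls are set aside.

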2.2. Endpoints

Primary efficacy endpoint

- Time to sustained withdrawal of supplementary oxygen (11-category WHO Clinical Progression Scale ≤ 4) with no subsequent reutilisation during remaining study period (See [Appendix 13 - World Health Organization \(WHO\) Clinical Progression Scale](#)).

Key secondary efficacy endpoint

- Time to sustained (i.e., with no subsequent readmission to Day 31) hospital discharge (since randomisation).

Secondary endpoints

Efficacy:

- Clinical status, as assessed by the 11 category WHO Clinical Progression Scale, at Day 8 (± 1) (See [Appendix 13 - World Health Organization \(WHO\) Clinical Progression Scale](#)).
- Total duration of advanced oxygen support (high-flow nasal oxygen, extracorporeal membrane oxygenation -ECMO-, non-invasive ventilation or mechanical ventilation).
- Percentage of patients in each study group requiring admission to ICU on Days 4, 8, 15, and 31.

Safety/tolerability:

- Frequency of TEAEs;
- Frequency of TEAEs of ≥ 3 according to NCI-CTCAE v5.0;
- Frequency of treatment-emergent adverse events of special interest (AESIs);
- Frequency of serious adverse events (SAEs);
- Frequency of drug-related serious adverse events (i.e., SARs);
- Frequency of adverse events leading to treatment discontinuation;
- Frequency of deaths;
- Change respect to baseline in individual study-defined laboratory parameters (See [Section 7.2.4.](#));
- Change respect to baseline in individual vital signs (See [Section 7.2.5.](#));
- Change respect to baseline in individual study-defined ECG parameters (See [Section 7.2.5.](#)).

Other secondary endpoints

- Percentage of patients in each study group requiring hospital readmission due to COVID-19-related signs or symptoms through Day 31.

- Percentage of patients in each study group and in each of the categories of the 11-category WHO Clinical Progression Scale on Days 4, 8, 15 and 31 (See [Appendix 13 - World Health Organization \(WHO\) Clinical Progression Scale](#)).
- Percentage of patients in each study group requiring oxygen therapy on Days 4, 8, 15 and 31.
- Time to intensification of respiratory support (WHO >6 [intubation]) (See [Appendix 13 - World Health Organization \(WHO\) Clinical Progression Scale](#)).
- Total duration of intensive care unit (UCI) stay for each study group.
- Percentage of patients in each study group requiring high-flow oxygen on Days 4, 8, 15, and 31.
- Percentage of patients in each study group requiring non-invasive mechanical ventilation on Days 4, 8, 15, and 31.
- Percentage of patients requiring either extracorporeal membrane oxygenation ECMO or invasive mechanical ventilation by Days 4, 8, 15, and 31.
- Time to initiation with immune-modulating drugs.
- Time to initiation with antiviral drugs.
- Percentage of patients receiving subsequent immune-modulating drugs on Days 4, 8, 15 and 31.
- Percentage of patients receiving subsequent antiviral drugs on Days 4, 8, 15 and 31.
- Percentage of patients in each study group with nosocomial infection by Days 4, 8, 15 and 31.
- Mortality in each study group on Days 4, 8, 15 and 31.
- Change in SARS-CoV-2 viral load in each study group from Day 1 before administration of the study drug until Day 8.
- Percentage of patients in each study group with undetectable SARS-CoV-2 viral load on Day 8.
- Change in inflammatory biomarkers (C-reactive protein [CRP], ferritin, interleukin [IL]-6, IL-1 β , IL-10 and tumour necrosis factor alpha [TNF α]) in each study group from baseline until Days 2, 3, 4, 8, and 31.
- Change respect to baseline in individual serological assessments.
- Obesity, hypertension, age and individual co-morbidities included in the Charlson Index ([Appendix 11- Age-adjusted Charlson Index](#)), ISARIC-4C score ([Appendix 14 - ISARIC 4C Mortality & 4C Deterioration Scores](#)), or vaccination status.
- Time to sustained withdrawal of supplementary oxygen (11-category WHO Clinical Progression Scale \leq 4) with no subsequent reutilisation during remaining study period, before (protocol v.6) and after the amendment (protocol v.7).
- Time to sustained (i.e., with no subsequent readmission to Day 31) hospital discharge (since randomisation), before (protocol v.6) and after the amendment (protocol v.7).

Additionally, a dedicated QTc substudy will be performed in a subset of approximately 50 patients with ECGs collected over Days 1 to 3 using Holter monitors to assess treatment impact on QTc prolongation. See [Appendix 8](#) for objectives and respective endpoints planned for the QTc substudy. The substudy patients will have blood sampling for pharmacokinetic assessments over Days 1 to 4.

